## **Project Overview**

Posttraumatic stress disorder (PTSD) affects approximately 23% of veterans and is associated with numerous negative mental health outcomes, including decreased quality of life, substantial impairments in work, home, and social functioning, increased risk of suicide, and poorer long-term physical health. Despite the existence of evidence-based treatments for PTSD, research has demonstrated that 14-50% of those receiving these gold-standard PTSD treatments either do not respond or exhibit a diminished treatment response. Consequently, there is a clear need to explore ways to improve existing treatment outcomes. Given the strong evidence supporting existing first-line treatments, such as Cognitive Processing Therapy (CPT), it is likely that augmenting these treatments with novel therapeutics that have shown promise in the treatment of other conditions can further enhance outcomes beyond each treatment alone. One such therapeutic is Stellate Ganglion Block (SGB), which has been safely used in the treatment of chronic pain and other conditions. SGB has recently been shown to be effective at reducing PTSD symptoms.

The proposed project will systematically test whether combining CPT with SGB produces greater PTSD symptom reductions and functional improvements in the short- and longer-term up to 6-months follow-up compared to CPT (+Placebo) or SGB (+Daily Monitoring) alone.

## **Scientific Review**

### ***First-Line PTSD Treatments***

PTSD is a debilitating mental health condition that impacts approximately 23% of Veterans. Between 2001-2017, the average incidence rate of PTSD in the U.S. military was 7.88 per 1000 service members, with a peak incident rate of 12.94. Moreover, PTSD is associated with high rates of comorbidity and high degrees of functional impairment, more so than any other mental health disorder. Untreated PTSD has been shown to lead to substantial impairments in work, home, and social functioning, increased risk of suicide, and poorer long-term physical health outcomes.

The Veterans Administration and Department of Defense (VA/DoD) Clinical Practice Guidelines recommend CPT, among other interventions, as a first-line psychotherapeutic intervention for the treatment of PTSD. CPT can produce large PTSD symptom reductions. These PTSD symptom reductions are lasting and can be maintained for 10 years or more. CPT has been successfully used with a wide range of populations, including service members and Veterans. The primary mechanism of action in CPT is hypothesized to be a reduction in negative trauma-related cognition about oneself, others, and the world.

While CPT is traditionally delivered weekly over 12 sessions, our research group and others have recently demonstrated that CPT can be successfully administered in as little as a single week. In our recently completed clinical trial we also demonstrated that 1-week massed CPT can be effectively delivered via telehealth. Completion rates for 1-week massed CPT were extremely high with 96% of participants completing the entire course of treatment, suggesting excellent feasibility. The results from the 1-week massed CPT trial suggest that 87% of study participants experienced clinically significant PTSD severity changes after the single week, with

the majority of participants experiencing clinically meaningful improvement in PTSD symptoms after the fourth session (i.e., after two days of treatment). Symptom reductions achieved throughout 1-week massed CPT were maintained at the 3-month follow-up. Importantly, participants found the extremely brief treatment helpful and reported that it helped them remain focused on the treatment and acquire the necessary skills to effectively manage their PTSD symptoms. We have also shown that the massed/daily delivery of CPT is feasible and effective at reducing PTSD symptom severity with gains maintained for at least 12 months.

### ***Non-Response to First-Line PTSD Treatments***

Despite the demonstrated effectiveness of first-line PTSD treatments, not all individuals who receive these treatments show a favorable response. Research has demonstrated that 14-50% of those receiving gold-standard first-line PTSD treatments either do not respond or exhibit a diminished treatment response. Other studies have suggested that approximately two-thirds of treatment completers continue to meet PTSD diagnostic criteria and therefore continue to be at risk for reduced work, home, and social functioning. Moreover, meta-analyses suggest that service members and Veterans are less responsive to first-line PTSD treatments compared to civilians. Based on these data, it can be expected that many service members and Veterans will retain their PTSD diagnosis following an initial course of a first-line PTSD treatment, highlighting the need to identify better treatment options.

### ***Stellate Ganglion Block May be a Promising Treatment Option***

The stellate ganglion (SG) is a collection of sympathetic nerves found at the level of the sixth and seventh cervical ganglion. The SG forms as a result of the fusion of the inferior cervical and first thoracic sympathetic ganglions. Clinical blockade of the SG is useful for a wide variety of diagnostic and therapeutic indications and is becoming a well-researched and well-established treatment for a variety of physical health concerns, including chronic pain. SGB has recently been shown to also be effective for reducing PTSD symptom severity. SGB is a treatment that involves an injection of local anesthetic around the stellate ganglion (located at the base of the neck) to block its transmission of pain signals.

A recent sham-controlled randomized clinical trial suggested that SGB produces significantly greater PTSD symptom reductions compared to saline injections. Similarly, case series studies and reviews support the safety and effectiveness of SGB in reducing PTSD symptoms. Studies have indicated that SGB's impact can last over time, although there is a clear need for studies that examine treatment effects for more than three months. SGB has been determined to be safe and is particularly well-received by military populations.

Research suggests that SGB may be particularly effective at reducing hyperarousal symptoms. This is particularly important because first-line psychotherapies have been shown to have a limited impact on hyperarousal symptoms. Combining CPT and SGB may therefore enhance the efficacy compared to each treatment used as a standalone intervention and provide a relief with common residual symptoms, such as irritability or angry outbursts, difficulty concentrating, and sleep disturbance.

Individuals with PTSD most notably reported significant enhancements in the initial week following the SGB procedure. This immediate post-procedural period might serve as an opportune

time to initiate trauma-focused psychotherapy. The initial symptom alleviation resulting from SGB could enhance individuals' receptivity to interventions like CPT. This heightened engagement, stemming from symptom reduction, might further catalyze cognitive and behavioral shifts in individuals. Such transformations could not only amplify the therapeutic outcomes beyond those achieved by standalone treatments but also ensure the longevity of these benefits.

### ***Complementary Treatment Mechanisms***

CPT and SGB are hypothesized to operate via distinct mechanisms that may complement one another in the treatment of PTSD. CPT is a primarily cognitive intervention that teaches individuals to identify negative posttrauma cognitions about the cause of the traumatic event (i.e., “It was my fault,” “If only I had done something differently the event wouldn’t have happened,” “If people had done their jobs, everyone would have survived”), as well as overgeneralized beliefs stemming from the trauma about themselves, others, and the world (i.e., “The world is unsafe,” “I can’t trust anyone,” “I am damaged”) and identify related emotions. These distorted beliefs are thought to fuel trauma-related symptoms and functional impairment.

The mechanism by which SGB exerts therapeutic effects in PTSD, on the other hand, is postulated to primarily revolve around the modulation of the sympathetic nervous system. The SG, located at the juncture of the cervical and upper thoracic vertebrae, serves as a critical nexus in sympathetic innervation, influencing various physiological functions. Upon administering SGB, a local anesthetic is delivered around the SG leading to an effective interruption of sympathetic outflow. This intervention is theorized to induce a subsequent reduction in overall sympathetic tone, diminishing the heightened state of arousal characteristic of PTSD. Beyond simple sympathetic downregulation, emerging research highlights potential neurochemical alterations secondary to SGB. Particularly, there may be modifications in neurotransmitter dynamics, with norepinephrine—a key sympathetic neurotransmitter that's often dysregulated in PTSD—being of primary interest. By modulating sympathetic activity, *SGB might catalyze a more adaptive form of neural plasticity, enabling neural circuits to reorient towards a more normalized state associated with fewer PTSD symptoms.*

### ***The Importance of Testing Combined CPT and SGB***

Taken together, evidence points to the ability of CPT and SGB to reduce the severity of PTSD symptoms in short periods via two distinct psychological (i.e., changes in trauma-related cognitions) and biological (i.e., sympathetic/parasympathetic balance) mechanisms. However, no studies to date have systematically examined whether combining these two interventions produces larger effects than each intervention alone. Consequently, there is a critical need to examine CPT and SGB in combination to determine whether this could have a positive impact on overall PTSD treatment response rates. Since both treatments are widely available, finding support for the hypothesis that CPT+SGB produces stronger outcomes than each treatment alone could result in rapid dissemination which may help a greater number of service members and Veterans experience larger improvements compared to each treatment alone as is the case in current practice.

### ***Measuring Physical Health Improvements via Heart Rate Variability***

SGB is theorized to exert a direct influence on the autonomic nervous system, predominantly through tempering the sympathetic nervous system's activity. The equilibrium between the sympathetic and parasympathetic arms of the autonomic nervous system is represented by a metric known as heart rate variability (HRV). HRV refers to the variation in time intervals between consecutive heartbeats. In essence, a higher HRV signifies greater adaptability and resilience of the heart, indicative of a harmonious balance between sympathetic and parasympathetic inputs. Numerous studies have unequivocally associated enhanced HRV with robust cardiovascular health, augmented physical stamina, and optimal physiological functioning. Moreover, lower HRV has been correlated with an array of adverse health outcomes, including increased susceptibility to cardiovascular disease and reduced life expectancy.

Despite the established connection between HRV and overall health as well as PTSD, there remains a paucity of research dissecting the direct influence of evidence-based psychotherapies (EBPs) for PTSD on HRV or broader physical health parameters. Evidence-based psychotherapies such as CPT have been predominantly investigated concerning their therapeutic efficacy on psychological parameters, with less emphasis on physiological outcomes. Therefore, it is paramount to discern if such psychotherapies can directly ameliorate physical health or if their positive repercussions on health are predominantly mediated by reductions in PTSD symptomatology.

## **Research Plan**

### **Objectives**

To systematically address questions surrounding improving PTSD treatment, the proposed 3-arm randomized controlled clinical trial will directly compare the combination of CPT+SGB vs. CPT (+Placebo) vs. SGB (+daily monitoring) in a total of 180 service members, Veterans, and civilians with PTSD. Short- and longer-term (up to 6-month follow-up) impacts of the respective interventions on both PTSD symptoms and functioning will also be assessed.

#### ***Objective 1***

Determine the efficacy of combining CPT and SGB for reducing PTSD symptoms and improving functioning. H1a: Participants who receive CPT+SGB will experience greater reductions in PTSD symptoms based on clinician-administered and self-reported PTSD assessments and greater improvements in functioning compared to each intervention alone. H1b: Clinician-administered and self-reported PTSD symptoms will reduce to a greater extent immediately after and 3- and 6-months following treatment for participants assigned to the CPT+SGB condition vs. those who receive CPT (+Placebo) and SGB (+daily monitoring).

#### ***Objective 2***

Probe changes in negative posttrauma cognitions and sympathetic/parasympathetic balance as potential complementary treatment mechanisms. H2a: Negative posttrauma cognitions will improve over the course of CPT+SGB and CPT and improve to a greater extent than for individuals who receive SGB. H2b: Greater reduction in the sympathetic/parasympathetic balance, assessed via heart rate variability (HRV), will be experienced by individuals assigned to the CPT+SGB and SGB conditions compared to individuals who receive CPT. H2c: Changed in negative posttrauma

cognitions and sympathetic/parasympathetic balance will predict short- and longer-term (6-month) PTSD symptom reductions and functional improvement.

### ***Secondary Objectives***

The study is also designed to examine the effects of each treatment on physical well-being, as assessed via heart rate variability (HRV), which has been closely linked to long-term physical health.

### **Target Population and Sample Size**

We will consent and enroll a total of approximately 180 service members, veterans, and civilians with PTSD. Based on our prior trials with this population, we anticipate that ~25-50% of potential participants will not meet inclusion criteria or will not start treatment. Thus, we plan to recruit 270 individuals to have a final sample of 180 service members, veterans, and civilians who start treatment. We will purposely oversample for veterans and service members with the goal of recruiting approximately  $n = 90$  veterans and/or service members and approximately  $n = 90$  civilians for the final sample.

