### **Inclusion and Exclusion Criteria**

Individuals are *eligible* for the current study if they:

1. Are 18 years or older
2. Are fluent in English
3. Have experienced a Criterion A traumatic event during their lifetime
4. Have a PTSD diagnosis verified via the Clinician Administered PTSD Scale for DSM-5
5. Have not previously received an SGB
6. Have a smartphone that they can use for the entire duration of the study
7. Are willing and able to receive 2 injections (SGB or placebo) 2 weeks apart at the Rush Pain Clinic
8. Are willing and able to participate in daily CPT or Daily Monitoring over the course of one week
9. Are willing and able to complete self-report measures and clinician-rated assessments at multiple time points over the course of the study

Individuals are *excluded* from the current study if:

1. The traumatic event occurred in the past month

2. They are currently suicidal or homicidal (i.e., plan and intent)
3. They have unmanaged psychosis or mania
4. They have not been on a stable dose of psychotropic medication for at least one month by the time of the baseline assessment or are planning to change their medications within 3 months of starting their participation in the study
5. They have completed an evidence-based cognitive behavioral PTSD treatment (e.g., CPT or Prolonged Exposure) in the past 3 months or are currently receiving an evidence-based PTSD treatment
6. They have an intellectual disability or significant cognitive impairment that would prevent them from engaging fully in treatment
7. They are currently on any blood-thinning medications or have a coagulopathy
8. They have any of the following conditions: a recent myocardial infarction, glaucoma, a pre-existing contralateral nerve palsy, severe emphysema, or a cardiac conduction blockade.
9. They are allergic to any of the medications injected (i.e., ropivacaine, lidocaine, propofol)
10. They have an active infection
11. They have a serious or unstable medical illness or instability for which hospitalization may be likely within the next year
12. They have a visual or auditory impairment that would prevent them from fully participating in study activities
13. They are involved with current legal actions related to the traumatic event that is anticipated to be targeted during treatment
14. They have substance dependence that, in the judgment of the Principal Investigator, may require hospitalization if substances were discontinued.

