### ***Informed Consent***

Informed consent will be obtained by trained members of the study staff before the baseline assessment. Potential participants will be emailed the electronic consent form via REDCap, a HIPAA-secure platform. Study staff will call and explain the study to the potential participants and answer any questions they have. Potential participants will be encouraged to carefully read the entire consent form and to take their time to consider if they would like to participate. Potential participants can take as much time as they need to decide if they would like to participate and reach out to study staff with any questions they may have. Potential participants will be allowed to discuss the study with others (e.g., an outside treatment provider) if they would like to before consenting.

If at any time reconsent is needed, participants will be sent a new electronic consent form via REDCap and study staff will inform them of any changes that were made.

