### ***Virtual Baseline Assessments***

Under the supervision of the Principal Investigator, who is a licensed clinical psychologist, trained study staff, with at least a Bachelor's degree and who are not providing the treatment, will conduct structured diagnostic interviews. These interviews are to determine eligibility by confirming a diagnosis of PTSD, as assessed by a gold-standard Clinician Administered PTSD Scale for DSM-5. Completion of the baseline assessment will take approximately 4 hours and may take place over 1-2 days, depending on the participant's availability. The baseline assessment will be conducted virtually via the HIPAA-compliant telehealth platform Microsoft Teams. All baseline assessments will be audio/video recorded for research purposes and to ensure that assessments were delivered with fidelity.

Study staff will also securely email the full self-report assessment battery to intake participants via REDCap, which takes approximately 40 minutes to complete. Individuals who meet exclusion criteria during the virtual baseline visit or who choose not to participate will be referred for other treatment/resources as indicated.

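### Does the plan to recruit 270 people contradict the anticipated loss of about 25-50% and the target of 180 treatment starters?

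*Protocol*

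**What the plan says.** The Objectives section sets the size of the three-arm trial: "in a total of 180 service members, Veterans, and civilians with PTSD". Target Population and Sample Size opens with "We will consent and enroll a total of approximately 180 service members, veterans, and civilians with PTSD". It then gives the anticipated loss, "we anticipate that ~25-50% of potential participants will not meet inclusion criteria or will not start treatment", and concludes that "we plan to recruit 270 individuals to have a final sample of 180 service members, veterans, and civilians who start treatment". It also aims for about 90 veterans or service members and about 90 civilians in the final sample.

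Three other sections fix the order of events. Under Informed Consent, "Informed consent will be obtained by trained members of the study staff before the baseline assessment". Under Virtual Baseline Assessments, "These interviews are to determine eligibility by confirming a diagnosis of PTSD", and "Individuals who meet exclusion criteria during the virtual baseline visit or who choose not to participate will be referred" elsewhere. The diagnosis confirmed at that interview is itself an inclusion criterion: "Have a PTSD diagnosis verified via the Clinician Administered PTSD Scale for DSM-5".

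Recruitment Methods adds that recruitment success is reviewed every quarter, that the team will discuss changes of strategy if problems arise, and that a recruitment firm will be engaged.

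**The concern.** Two things look wrong.

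First, 270 is presented as the consequence of a 25-50% loss, yet neither end of that range nor its midpoint produces it. Losses between 33.3% and 50%, about two thirds of the width of the range, would leave 270 recruits short of 180 starters. A trial that stopped there would be smaller than the Objectives state.

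Second, about 180 is used both for people who consent and for people who start treatment. Because eligibility is confirmed after consent, some people who consent will be found ineligible or will not start. If enrolment were closed at about 180 consents, any such loss would take the number of starters below 180.

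**Working it through.** **Inputs**, all from Target Population and Sample Size: 180 treatment starters, 270 recruits, anticipated loss d of about 25-50%.

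**The plan's own figure.** Recruits needed = 180/(1 - d). Setting this equal to 270 gives d = 1 - 180/270 = 33.3%. So 270 is reproduced at one loss rate, which is not stated but lies inside the stated range.

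**Across the range:**

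| Loss | Recruits needed for 180 starters | Starters from 270 recruits |
|---|---|---|
| 25% | 180/0.75 = 240 | 270 × 0.75 = 202.5 |
| 33.3% | 180/0.667 = 270 | 270 × 0.667 = 180 |
| 37.5% (midpoint) | 180/0.625 = 288 | 270 × 0.625 = 168.75 |
| 50% | 180/0.50 = 360 | 270 × 0.50 = 135 |

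**Was a formula misapplied?** 180 × (1 + 0.50) is also 270, which would be the wrong way to inflate for a 50% loss. But 33.3% loss with the correct formula gives the same number, and the protocol does not say how 270 was obtained. The match cannot show an error.

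**Worst case.** With 50% loss and recruitment halted at 270, there would be 180 - 135 = 45 fewer starters (25%). Standard errors would be √(180/135) = 1.155 times as large, about 15% more, under a fixed allocation. Each of the veteran and civilian groups would hold about 135/2 = 67.5 against the goal of about 90. Both conditions are needed. The protocol states no cap at 270, and its quarterly review is the provision for recruitment that falls behind.

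**The two uses of 180.** The opening sentence attaches about 180 to those consented and enrolled; the recruitment sentence attaches 180 to those who start treatment. Consent comes before the baseline interview, so read literally the two agree only if nobody is lost after consent. The protocol gives no rate for that loss. If it were 5%, 10% or 20% (assumed values), 180 starters would need 180/0.95 = 189.5, 180/0.90 = 200 or 180/0.80 = 225 consents. Yet the opening sentence describes people with PTSD, a diagnosis verified only at baseline. It therefore reads most naturally as describing the enrolled sample, and the same section goes on to define the final sample as treatment starters.

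**Where the 270 are counted.** The loss is applied to potential participants. Informed Consent uses that term for people who have not yet consented, and Eligibility Phone Screening comes before consent. The natural reading is that the 270 are counted before consent, though the exact step is not given.

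**The case for a change.** The best case for a change is that the protocol draws a single number from a range that the number only partly covers, names no planning rate, and gives 180 two meanings in one section. These are figures the protocol states itself, so they cannot be put down to detail left for an analysis plan. Since the PTSD diagnosis can be verified only after consent, loss after consent cannot be taken as zero. Consent totals are also tracked in practice, so the consent figure should not equal the starter figure. A sentence or two would settle it.

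Part of this stands. The wording on consents is loose, the rate behind 270 has to be worked out by the reader, and 270 would not be enough at losses above 33.3% unless recruitment went on. But a planning value chosen inside an approximate range contradicts nothing, and dividing 180 by 270 recovers the rate. The harm comes only from a stopping rule, at 270 recruits or at 180 consents, that the protocol does not contain.

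**Conclusion.** The concern does not call for a change. The figure of 270 corresponds to 33.3% loss, inside the anticipated 25-50%, and lies within the implied 240-360 recruits. A team following the protocol aims for 180 people who start treatment, watches recruitment each quarter and can adjust if loss runs high. The 135-starter figure and the 15% increase in standard errors describe a halt that is not planned. The protocol shows no power calculation, so no loss of power can be derived, and randomisation and endpoints are untouched.

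The double use of about 180 is a clerical looseness that the section itself resolves by defining the final sample as those who start. Rewording it would write down an assumption without altering any result. This conclusion rests on reading 180 as treatment starters and on there being no cap on recruitment, as the protocol's silence on a cap and its quarterly review suggest.
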